4.2.3 General Imputation Rule for Incomplete Dates

Where necessary for the calculation of derived variables (e.g., age), partial dates will be imputed using the earliest calendar date based on the partial date provided. This rule is valid for all partial dates with the exception of the following:

- Start and stop dates of AEs
- Start and stop dates of prior and concomitant medication
- Stop dates of past and concomitant diseases
- Patch application dates

Completely missing dates will not be replaced, and the corresponding derived variables will be set to missing.

4.3 Interim analyses and data monitoring

Due to early stopping of the study, the interim analyses will no longer be performed.

4.4 Multicenter studies

Not applicable.

4.5 Multiple comparisons/multiplicity

Not applicable.

4.6 Use of an efficacy subset of subjects

Not applicable.

4.7 Examination of subgroups

Not applicable.

5 STUDY POPULATION CHARACTERISTICS

5.1 Subject disposition

Subject disposition will be presented for the RS in terms of the number of subjects who

- completed or withdrew (including reasons) during the study
- started the Titration Period (attended Visit 2 and was treated) and subsequently completed (attended Visit 5) or withdrew (including reasons) during the Titration Period

- started the Maintenance Period (attended Visit 6) and either completed or withdrew (including reasons) during the Maintenance Period
- started the Taper Period and completed (attended Visit 10) or withdrew (including reasons) during the Taper Period.

Subjects will be counted as completed study and maintenance period, if they don't withdraw before EoM, and as completed titration/taper period, if they don't withdraw before the end of the titration/taper period.

Summaries will also be provided for discontinuations due to AEs and disposition of analysis sets.

Reasons for screen failure will be listed for the ES.

5.2 Protocol deviations

The subject incidence (and percentage) of important protocol deviations will be summarized both overall and by treatment group for the RS. These summaries will also be provided by site.

All important protocol deviations will also be listed for the RS.

6 DEMOGRAPHICS AND OTHER BASELINE CHARACTERISTICS

6.1 Demographics

Age will be derived in years applying all rules for missing date imputation as described in [Section 4.2.3](#) as integer $((\text{Date of informed consent} - \text{date of birth}) / 365.25)$.

Weight recorded in pounds (lb) will be converted to kilograms (kg) as $\text{weight}(\text{lb}) * 0.4536 \text{ kg/lb}$.

Height recorded in inches (in) will be converted to height in centimeters (cm) as $\text{height}(\text{in}) * 2.54 \text{ cm/in}$.

The BMI will be calculated as $\text{weight}(\text{kg}) / (\text{height}(\text{m}))^2$.

The following demographics will be summarized for the RS:

- Age (years)
- Age (EudraCT age categories)
- Age (clinicaltrials.gov age categories)
- Gender (Male; Female)
- Racial Group (American Indian/Alaskan Native; Asian; Black; Native Hawaiian or Other Pacific Islander; White; Other/Mixed)
- Ethnicity (Hispanic or Latino; Not Hispanic or Latino)
- Weight (kg)
- Height (cm)
- BMI (kg/m^2)

- BMI (<18.5, 18.5-<25, 25-<30, 30-<35, 35-<40, >=40, Missing)

6.2 Other Baseline characteristics

Time since diagnosis of RLS will be derived in years applying all rules for missing date imputation as described in [Section 4.2.3](#) as integer ((date of informed consent - date of diagnosis) / 365.25).

The following Baseline characteristics will be summarized for the SS:

- Time since diagnosis of RLS (years)

Other Baseline characteristics (e.g., lifestyle items) will be listed.

6.3 Medical history and concomitant diseases

Previous and ongoing diseases will be derived from the medical history form of the eCRF.

Medical history (except RLS) will be presented for the SS, summarized by MedDRA System Organ Class (SOC) and preferred term (PT).

Procedure history and concomitant medical procedures will be listed. Family medical history will be collected only when PDILI is reported and will be provided in a listing.

6.4 Prior and concomitant medications

Medications will be considered as prior if the start date of the medication is before the date of first patch administration. Medications will be considered as concomitant if it was taken at least once in the Treatment Period starting with the first patch administration and ending the day of last patch removal during the study. Medications starting prior to first patch application and continuing into the Treatment Period will be considered both prior and concomitant medication.

For cases of partial or missing dates the rules described in [Section 4.2.2](#) will be applied.

Prior and concomitant medications will be summarized for the SS. The number and percentage of subjects who used prior or concomitant medications, respectively, will be presented according to the Anatomical Therapeutic Chemical main group, the Pharmacological subgroup, and the preferred drug name.

7 MEASUREMENTS OF TREATMENT COMPLIANCE

Compliance will not be calculated for the early study termination scenario. Refer to [Section 10.1](#) for information about study medication exposure.

8 EFFICACY ANALYSES

If not stated otherwise, all efficacy analyses will be performed for the FAS.

8.1 Statistical analysis of the primary efficacy variables

The co-primary efficacy variables are change from Baseline to EoM in IRLS sum score and change from Baseline in CGI Item 1 to EoM.

8.1.1 Derivations of primary efficacy variables

The IRLS consists of 10 questions, each using a 5-point scale ranging from 0=not present to 4=very severe. The IRLS sum score will be calculated by summing up the single scores of all

applicable questions, i.e., the sum score will range between 0 and 40. If any answer is missing, the IRLS sum score will also be missing.

The CGI item 1 (Severity of Illness) scale ranges from 0 to 7 as follows: : 0=not assessed, 1=normal, not ill at all, 2=borderline ill, 3=mildly ill, 4=moderately ill, 5=markedly ill, 6=severely ill, 7=among the most extremely ill.

8.1.2 Primary analysis of the primary efficacy variables

Observed results and changes from Baseline in IRLS sum score and CGI (Item 1) will be summarized by visit and by treatment group.

8.1.3 Secondary analyses of the primary efficacy variable

Not applicable.

8.1.4 Supportive and sensitivity analyses of the primary efficacy variable

Not applicable.

8.2 Statistical analysis of the secondary efficacy variables

All summaries and analyses of the secondary efficacy variables will be based on the FAS.

8.2.1 Restless Legs Syndrome-6 Rating Scales

The RLS-6 Rating Scales (Kohnen et al, 2003) is designed to assess the severity of RLS and consists of 6 subscales. The subscales assess severity of symptoms at the following times of the day/evening: falling asleep, during the night, during the day at rest, and during the day when engaged in daytime activities. In addition, the subscales assess satisfaction with sleep and severity of daytime tiredness/sleepiness. Scores for each of the 6 subscales range from 0 (completely satisfied/none /not at all) to 10 (completely dissatisfied/very severe).

The change from baseline will be derived for each of the 6 subscales. No sum score will be calculated.

Summary statistics for observed values as well as changes from Baseline by visit will be provided for each of the RLS-6 rating scales.

9 PHARMACOKINETICS

9.1 Plasma concentration

Plasma samples will be collected at Visit 6 and Visit 9. For subjects in the rotigotine groups, plasma concentrations will be listed.

9.2 Population Pharmacokinetics

The plasma concentrations of unconjugated rotigotine may also be used for population PK-PD analyses. Details and methods of these analyses will be described in the Data Analysis Plan and the results will be reported in a separate modeling report.

10 SAFETY ANALYSES

If not stated otherwise, all safety analyses will be conducted for the SS.

10.1 Extent of exposure

The duration of exposure will be calculated as (date of last patch removal – date of first patch application + 1 day).

All derivations of rotigotine doses given below are nominal doses, i.e., include placebo patches in the rotigotine 2mg/24h or placebo arm.

The final dose level ('final dose') is defined as the dose administered at the start of the Maintenance Period (i.e., at Visit 6) and intended to be used during the Maintenance Period. If the subject down titrates to the previous dose during the Titration Period and continues on that dose at Visit 6, then the back-titrated dose level is the 'final dose'.

The determination of the dose of longest duration is based on the entries given in the drug dosing log of the eCRF. The duration of a single dose will be calculated as the sum of the durations of each dosing interval with intake of the respective dose whereas the duration of each dosing interval will be calculated as (end date – start date + 1).

Where more than one dose has the same 'longest duration', the highest dose will be selected. For subjects who dropped out during the Titration Period, the last applied dose during the Titration Period will be used as dose of longest duration. If the dose of longest duration is 0mg/24h, but the subject was exposed at least once to active drug, the minimum active dose will be utilized.

Summary statistics will be presented for the following variables:

- Duration of exposure (days)
- Final dose (mg/24h) at the start of Maintenance (0 mg/24h, 1 mg/24h, 2 mg/24h and 3 mg/24h)
- Dose of longest duration (0 mg/24h, 1 mg/24h, 2 mg/24h and 3 mg/24h)

A listing of patch adhesiveness findings, including date and time of detachment, location and side of body, percent adherence and kit number will be provided.

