7.2 Treatments to be administered

7.2.1 Titration Period

The study will begin with a 3-week Titration Period, during which subjects will receive rotigotine patches in escalating weekly doses (from 1mg/24h to 2mg/24h for subjects randomized to 2mg/24h and from 1mg/24h to 2mg/24h to 3mg/24h for subjects randomized to 3mg/24h) until the randomized dose level (or matching placebo) is achieved (Table 7–2). During the Maintenance Period, the subject will continue as per the assigned treatment arm. Following the Maintenance Period, subjects will be de-escalated over 4 days.

Table 7–2: Dose titration schedule

	Rotigotine Nominal Dose (mg/24h)	Patch surface area (cm ²)
Week 1 (Days 1 to 7)	1	1 x 5cm ² Active OR 1 x 5cm ² Placebo
Week 2 (Days 8 to 14)	2	1 x 10cm ² Active OR 1 x 10cm ² Placebo
Week 3 (Days 15 to 21)	3	1 x 5cm ² Placebo + 1 x 10cm ² Active OR 1 x 5cm ² Active + 1 x 10cm ² Active OR 1 x 5cm ² Placebo + 1 x 10cm ² Placebo

Subjects will be allowed to back-titrate 1 dose level during the Titration Period. Subjects are to complete the Titration Period at the back-titrated dose level and remain at this dose level for the

duration of the Maintenance Period. If AEs occur during the Titration Period that are thought to be the result of excessive dopaminergic stimulation (eg, intolerable nausea/vomiting), subjects should be back-titrated to their previous dose level and commence the Maintenance Period immediately. Visits will be scheduled every week during the Titration Period. If subjects withdraw due to lack of efficacy, they are eligible to roll over to the open-label study, RL0007, after the 3 weeks of the Titration Period are completed.

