7.2.1.1 Maintenance Period

The Titration Period will be followed by a 12-week Maintenance Period. Subjects will maintain doses achieved at Visit 6 (end of the Titration Period) throughout the Maintenance Period. During the Maintenance Period, visits will be scheduled every 4 weeks for 3 visits.

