7.2.1.2 Taper Period

At the end of the Maintenance Period, subjects will enter a Taper Period lasting up to a maximum of 4 days (de-escalation of study medication) (Table 7-3). Subjects in the 2mg/24h arm and the 3mg/24h arm will taper down to 1mg/24h by the end of the Taper Period. Subjects in the placebo arm will continue placebo throughout the 4-day Taper Period. At the end of the Taper Period, subjects will be contacted by telemedicine call.

Table 7-3: Dose down titration schedule

Rotigotine nominal dose (mg/24h)	Days	Patch surface area (cm ²)
Placebo	107 and 108	1 x 5cm ² Placebo + 1 x 10cm ² Placebo
	109 and 110	1 x 5cm ² Placebo + 1 x 10cm ² Placebo
1	107 and 108	1 x 5cm ² Active + 1 x 10cm ² Placebo
	109 and 110	1 x 5cm ² Active + 1 x 10cm ² Placebo
2	107 and 108	1 x 5cm ² Active + 1 x 10cm ² Placebo
	109 and 110	1 x 5cm ² Active + 1 x 10cm ² Placebo
3	107 and 108	1 x 5cm ² Placebo + 1 x 10cm ² Active
	109 and 110	1 x 5cm ² Active + 1 x 10cm ² Placebo

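### Does SAP 10.1 leave it open whether the exposure table shows patch step or active rotigotine dose?

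*SAP*

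**What the plan says.** SAP 10.1 opens its dose derivations with a definition: "All derivations of rotigotine doses given below are nominal doses, i.e., include placebo patches in the rotigotine 2mg/24h or placebo arm". It takes the final dose at Visit 6 and says which level applies after back-titration: "If the subject down titrates to the previous dose during the Titration Period and continues on that dose at Visit 6", the back-titrated level is the final dose. Dose of longest duration comes from the eCRF dosing log; for subjects who drop out in Titration, "the last applied dose during the Titration Period will be used as dose of longest duration". Both rows share one set of categories: "Final dose (mg/24h) at the start of Maintenance (0 mg/24h, 1 mg/24h, 2 mg/24h and 3 mg/24h").

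The protocol uses the term nominal dose in two tables.

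- Table 7-2 (Section 7.2.1) gives Week 3 the single nominal dose 3 for all three patch sets, including "1 x 5cm ² Placebo + 1 x 10cm ² Placebo".
- Table 7-3 (Section 7.2.1.2), whose first column is headed "Rotigotine nominal dose (mg/24h"), puts that same pair of placebo patches in a row called Placebo. Its other rows are 1, 2 and 3.

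Protocol 7.2.1.1 carries the Visit 6 level forward: "Subjects will maintain doses achieved at Visit 6 (end of the Titration Period) throughout the Maintenance Period".

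**The concern.** Two readings seem possible. Counting every patch (patch step) puts all subjects who are not back-titrated at 3 mg/24h. Counting active patches only (active content) puts them at 0, 2 or 3 by arm. The words of the definition favour patch step. The 0 mg/24h final-dose category and the Placebo row of Table 7-3 favour active content.

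Two programmers could therefore produce different tables. An entry of 3 in the 2mg/24h column might be taken for misallocation, because 3 mg/24h is a real study dose, when it would mean only that the subject was not back-titrated. These rows are also the only tabulated dose-level summary left: "Compliance will not be calculated for the early study termination scenario" (SAP 7), and plasma concentrations are only listed (SAP 9.1).

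**Working it through.** **Inputs.** Patch content: 5cm² = 1 and 10cm² = 2 mg/24h (Protocol Table 7-1). Patch sets by week and arm: Table 7-2. Taper sets: Table 7-3. Rules for the two rows: SAP 10.1. Planned days: 1-7, 8-14, 15-106, and taper 107-110. Assumption: back-titration returns a subject to the preceding row of Table 7-2 within the same arm.

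**Formulas.** Patch step = sum of nominal content over all patches worn. Active content = the same sum over active patches only.

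**Reproducing Table 7-2.** Week 3 patch step is 1 + 2 = 3 in every arm, which is the protocol's figure. Weeks 1/2/3 give patch step 1/2/3 in every arm. Active content is 0/0/0 (placebo), 1/2/2 (2mg/24h) and 1/2/3 (3mg/24h).

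**Final dose, patch step v active content**

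| Pattern | Placebo | 2mg/24h | 3mg/24h |
|---|---|---|---|
| Not back-titrated | 3 v 0 | 3 v 2 | 3 v 3 |
| Step 3 to 2 | 2 v 0 | 2 v 2 | 2 v 2 |
| Step 2 to 1 | 1 v 0 | 1 v 1 | 1 v 1 |

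The readings differ in 3 + 1 + 0 = 4 of 9 cells. These are possible patterns, not subject counts.

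**What each reading keeps.** Patch step separates all three patterns in every arm. Active content separates 1 of 3 on placebo (always 0), 2 of 3 in the 2mg/24h arm (2, 2, 1) and 3 of 3 in the 3mg/24h arm. Within a randomized column, the active final dose follows from the patch step: 0 on placebo, the smaller of step and 2 in the 2mg/24h arm, and the step itself in the 3mg/24h arm. The reverse is not possible in the first two arms.

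**Dose of longest duration, planned schedule, no back-titration.** Every taper set in Table 7-3 is one 5cm² plus one 10cm² patch, so patch step stays at 3 to Day 110.

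- Patch step, every arm: 7 days at 1, 7 days at 2, and 92 + 4 = 96 days at 3. 96/110 = 87.3%, so the entry is 3.
- Active content: placebo has 110 days at 0; the 2mg/24h arm has 7 + 4 = 11 days at 1 and 7 + 92 = 99 days at 2; the 3mg/24h arm has 7 + 2 = 9 days at 1, 9 days at 2 and 92 days at 3. The entries are 0, 2 and 3.
- Early leavers on patch step: last dosing day 15-21 is a Titration dropout, so the last applied dose is 3. At Day 22 there are 8 days at 3 against 7 and 7, so again 3. A Week 1 or Week 2 dropout is entered at 1 or 2 and has no final dose.

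**Where a 0 can come from.** SAP 10.1 has a rule for a subject whose longest-duration dose is 0 but who received active drug at least once. In the rotigotine arms active content is never 0 while patches are worn, so that 0 is most naturally a logged interval without a patch. This gives the 0 category a use in the longest-duration row on the patch-step basis too. In the final-dose row it has no evident use and looks like the same list repeated.

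**The case for a change.** The strongest case for a change is that one term has two meanings in the protocol and that the SAP's final-dose categories do not fit its own definition. With compliance dropped, a reader has no other dose-level table to check against. The remedy would be cheap: name active content as the basis and add a patch-step row.

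Part of this stands. The 0 mg/24h final-dose category is out of place, and an unlabelled 3 in the 2mg/24h column could puzzle a reader.

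The rest carries less weight. The definition in SAP 10.1 is explicit, and a column heading in a protocol taper table, to which 10.1 does not refer, does not override it. An empty category does no harm. Making active content the main basis would reverse what the text says and hide back-titration on placebo and, from step 3, in the 2mg/24h arm, although 10.1 defines final dose so as to show it. SAP 3.1 and 3.9 provide for all documented and calculated data to be listed, so dose histories remain open to inspection.

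**Conclusion.** No change to the plan follows. SAP 10.1 states a usable basis, consistent with Table 7-2, and patch step is a defensible choice because it preserves the back-titration information. What remains is a loose category list and a label, which the programmer and study statistician would ordinarily settle in the table itself.

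The reach is two descriptive rows. By SAP 3.1 the columns are randomized arms, so a 3 under placebo is unlikely to be taken for rotigotine exposure. Duration of exposure, the TEAE tables and the efficacy summaries do not use this derivation, and efficacy is descriptive only after early termination (SAP 8.1.2).

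On the planned numbers, the two arms in which the readings can differ hold 2 x 45 = 90 of 135 evaluable subjects. The number actually treated is not in the documents. Neither are the eCRF dosing log and the table shells, so the final row labels cannot be judged. The day counts assume the planned schedule; visit windows could shift them.

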10.2 Adverse events

Adverse events will be documented throughout the entire study on an ongoing basis. TEAEs are defined as events that started during the Treatment Period or within 30 days following the end of the Treatment Period (i.e., on or after the date of first patch application and within 30 days following the date of last patch removal) or any unresolved event already present before administration of treatment that worsens in intensity following exposure to the treatment. For AEs with a partial or missing start date, the imputation rules as described in [Section 4.2.2](#) will be applied.

Adverse events with a missing start date are defined as treatment-emergent if the end date of the AE is not on or before the date of first patch application.

An AE with action taken regarding study medication reported on the AE page of the eCRF as “drug permanently withdrawn” will be regarded as an AE leading to discontinuation of study medication.

Adverse events which have the question “Serious Adverse Event?” answered “yes” or missing are considered serious.

Treatment emergent AEs will be tabulated by MedDRA SOC, High Level Term (HLT) and PT. The number and percentage of subjects experiencing each event at least once will be summarized in addition to the number of events. In summaries of TEAEs by relationship and intensity, respectively, the number of events will not be presented.

All summaries will be sorted alphabetically by SOC and HLT and by frequency of events (PT) in the total rotigotine group within HLTs. If there is more than one PT with the same frequency in the total rotigotine group these events will be sorted alphabetically.

An overview of the incidence and frequency of all TEAEs, serious TEAEs, TEAEs leading to discontinuation of study medication, related TEAEs, severe TEAEs, all deaths and TEAEs leading to death will also be provided.

The following tabular summaries will be presented also.

- TEAEs
- TEAEs by intensity
- TEAEs by maximum intensity
- TEAEs by relationship to study medication per the Investigator
- Serious TEAEs
- Serious TEAEs by Relationship to study medication per the Investigator
- non-serious TEAEs above reporting frequency threshold of 5%

Individual subject data listings will be presented for all AEs.

